8 STATISTICS AND ANALYSES

8.1 Sample Size

Stage 1

We will recruit a minimum of 24 participants and 3 therapists from NHS sites, and a minimum of 6 participants and 1 therapist from a community provider linked to an NHS Trust.

Stage 2

We will recruit a minimum of 60 patients and 10 therapists.

8.2 Data Analysis

Outcome hierarchy

Primary outcomes: ODI walking item and the 6-minute walk-test

Secondary outcomes listed in order of priority: ODI standing item, ODI pain item, ODI overall, followed by all remaining outcome measures.

Stage 1

We will use a synthetic control method to evaluate the probability that the optimisation has improved the intervention (20). Synthetic controls are a method of using historical control data, and contemporary data on the natural history of a condition, to form the counterfactual element needed to draw inferences on the improvement cycles. The counterfactual state is one which estimates what would happen if the improvements were not made, or no intervention was made. The rich data set from the BOOST trial will allow us to create a counterfactual that accounts for context, and to draw a comparison with the BOOST group intervention as well as a comparison to the control arm of the BOOST trial (best practice advice).

Two different analytical approaches will be used to enable synthetic control comparisons. First, propensity score methods will be employed to balance measured covariates at baseline between the group receiving the optimised programme and the control arm of the BOOST trial (21). We will consider a broad list of demographic and baseline clinical characteristics as covariates. The effectiveness of the optimised intervention will be estimated in generalised linear mixed models for the study outcome measures with inverse probability of treatment weighting (IPTW) on the propensity score (PS). Previous studies have shown that IPTW can produce valid estimates of treatment effects in small samples if relevant confounders are included in the PS model, but sensitivity analyses will be conducted to explore the impact of model specification and missing data (22). Random effects will be included to account for any heterogeneity in response due to the recruitment centre. As a second approach, Bayesian hierarchical linear models will be used to compare the optimised intervention to each arm of the BOOST trial, with commensurate and power priors to determine the degree of borrowing of information from the historical trial data. Models will be adjusted for key baseline characteristics to account for measured confounders (23). We will guard against baseline differences generating confounded effect estimates by recruiting in a similar way to the original trial and ensuring a representative population.

Evidence from the counterfactual analyses will help inform assessment of whether the improvements in the intervention should be accepted. An attraction of the Bayesian framework is that it provides a

basis for making direct probability statements about whether a greater proportion of people achieve clinically significant outcomes in pain and walking with the improvements.

Data from the wrist worn accelerometer will be merged into the study dataset with all other participant outcome measures and will be included in the statistical modelling detailed above. We will also report descriptive summaries of all participant outcome measures.

Final decisions

Using data from a relatively smaller number of participants will not be definitive but will be reasonable to inform clinical practice. If our estimates from the propensity score analysis demonstrate that the point estimate of the optimised intervention is lying within the upper half of the distribution of the confidence interval of the original trial, we will take that as a positive marker. We will also consider the estimated posterior probability that the optimised intervention has improved outcomes from the Bayesian analysis and accept the new intervention if this is above 50%. If this probability estimate is below 50% or the point estimate from the propensity score analysis is lying below the original lower limit, then we will continue with the original intervention. If the two analyses diverge, the Bayesian approach will be taken as the primary analysis as it will be more sensitive. We will use qualitative interviews from the therapists delivering the optimised programme to determine whether the changes are manageable and appear effective. We will triangulate this data.

Stage 2: patient participant outcomes

We will collect outcome data from a minimum of 60 participants and follow the same data analysis plan as described for Stage 1. For implementation to be deemed successful and be launched widely via the FutureLearn BOOST MOOC, using comparison to the synthetic controls from the original trial, the benchmark will be that the estimates of changes in pain-related disability and walking are not significantly worse than the original trial.

Stage 2: therapist participant outcomes

Data will be analysed descriptively using IBM SPSS Statistics, version 28.0.1.0. Cases with missing values will excluded using listwise deletion. Free text responses will be coded using the TDF.

Interview studies (stage 1 and 2)

The interview studies in stage1 and 2 are separate studies but will follow the same analysis methods. Data will be analysed using framework methodology. The first stage of analysis is familiarisation of the raw data, listening to audiotapes and reading transcripts, to identify key ideas and recurrent themes (18). Data will then be coded and charted into a matrix under the four constructs of the Promoting Action on Research Implementation in Health Services (i-PHARIS) framework (context, innovation features, individual characteristics, and implementation processes) (15). Charting refers to the rearrangement and summarisation of data, with each column being a theme (i-PHARIS construct) and each row being a case (therapist interviewed) (18). To provide further granularity, data within each of the i-PHARIS constructs will be independently categorised by two members of the research team into determinants of behaviour change using the Theoretical Domains Framework (TDF) (19). The TDF consists of a set of 14 domains covering the main factors believed to influence clinicians' behaviour change, for example, knowledge, skills, beliefs about capabilities, beliefs about consequences, optimism, and professional identity (19). This framework has been well validated and applied successfully in both primary and secondary care contexts (24, 25). Any differences in coding will be resolved through discussion between the two researchers.

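### The propensity analysis contrasts optimised BOOST only with the advice arm, and judges it against original BOOST by placing a point estimate in the old trial's interval

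*Protocol*

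**What the plan says.** All of this is in Protocol section 8.2.

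- **Comparisons promised.** Under Stage 1, the historical trial data are to be used "to draw a comparison with the BOOST group intervention as well as a comparison to the control arm of the BOOST trial".
- **Propensity part.** Propensity methods are used "to balance measured covariates at baseline between the group receiving the optimised programme and the control arm of the BOOST trial". No other propensity comparator is named. On the contents of the score: "We will consider a broad list of demographic and baseline clinical characteristics as covariates". Outcomes are then analysed in mixed models with inverse probability of treatment weights.
- **Bayesian part.** "Bayesian hierarchical linear models will be used to compare the optimised intervention to each arm of the BOOST trial".
- **Decision rule.** Under Final decisions, the propensity result is a positive marker if the "point estimate of the optimised intervention is lying within the upper half of the distribution of the confidence interval of the original trial". The optimised programme is accepted if the posterior probability of improvement exceeds 50%. If that probability is below 50%, or if "the point estimate from the propensity score analysis is lying below the original lower limit, then we will continue with the original intervention". A further sentence makes the Bayesian analysis primary when the two diverge.
- **Stage 2.** The Stage 1 analysis plan is reused. The benchmark for wide launch is that changes in pain-related disability and walking are not significantly worse than in the original trial.

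**The concern.** The counterfactual for Stage 1 is what would have happened without the changes, that is, original BOOST. The propensity analysis estimates something else: optimised BOOST minus advice. The comparison that matters is then made informally, by reading one point estimate against an interval from another study.

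That interval describes the uncertainty of original BOOST minus advice. It does not contain the error of a cohort of 24 to 30 patients, which is the larger source. Nor does it allow for weighting moving the optimised-versus-advice estimate to a population other than the one in which the trial estimate was made.

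The rule has consequences. An estimate below the lower limit is written as a sufficient reason to stay with the original programme, so chance alone can trigger it. In Stage 2 the benchmark is a statement about a difference from the original trial, and the propensity analysis as described yields no standard error for that difference.

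**Working it through.** The protocol gives no power calculation, outcome SD or original arm sizes, so there is no planned figure to reproduce. The check below shows how the stated rule behaves under stated assumptions.

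**Inputs from the Protocol.** Stage 1 size: 24 in the Study Summary and section 2. Section 8.1 reads as 24 NHS plus 6 community patients, so 24 + 6 = 30. Stage 2 size: 60.

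**Assumptions.** Outcome SD 1, oriented so that higher is better. Original BOOST arm nB = 100–300 and advice arm nA = 100–200. Normal theory, no confounding, every patient counting fully.

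**Step 1: what the rule tests.** Let O, B and A be the mean outcomes on optimised BOOST, original BOOST and advice. The propensity estimate is O − A and the midpoint of the trial interval is B − A. Without reweighting, the advice arm cancels: (O − A) − (B − A) = O − B. So the rule is an indirect look at O − B, with

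- SE(O − B) = √(1/n + 1/nB)
- trial interval half-width h = 1.96 × √(1/nB + 1/nA)

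The rule uses h and never uses SE(O − B).

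**Step 2: numbers for n = 24.**

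| nB, nA | h | SE(O − B) | Equal: below lower limit, Φ(−h/SE) | Equal: inside upper half | 0.2 SD worse: midpoint or higher, Φ(−0.2/SE) |
|---|---|---|---|---|---|
| 100, 100 | 0.277 | 0.227 | 11% | 39% | 19% |
| 200, 100 | 0.240 | 0.216 | 13% | 37% | 18% |
| 200, 200 | 0.196 | 0.216 | 18% | 32% | 18% |
| 300, 200 | 0.179 | 0.212 | 20% | 30% | 17% |

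Worked example, last row: h = 1.96 × √(1/300 + 1/200) = 0.179; SE = √(1/24 + 1/300) = 0.212; Φ(−0.179/0.212) = Φ(−0.84) = 20%.

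Under equality the estimate reaches the midpoint or higher 50% of the time in every row. By symmetry it exceeds the upper limit as often as it falls below the lower one, 11–20%. Read literally, those best results lie outside the interval and so are not in its upper half.

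**Step 3: other sizes, same assumptions.** With n = 30, a truly equal programme falls below the lower limit 9–18% of the time, and one 0.2 SD worse reaches the midpoint or higher 15–17% of the time. With n = 60 the figures are 4–10% and 8–11%.

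**Step 4: the direct contrast.** The 95% half-width for O − B is 1.96 × SE: 0.42–0.45 SD with 24 patients (1.96 × 0.212 to 1.96 × 0.227) and 0.28–0.32 SD with 60 (1.96 × 0.141 to 1.96 × 0.163). The interval used as the yardstick has a half-width of only 0.18–0.28 SD.

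**Step 5: the decision sentences side by side.** Suppose the posterior probability is above 50% and the propensity estimate is below the original lower limit. The sentence joined by *or* says to keep the original. The divergence sentence says the Bayesian result governs, which means acceptance. Both cannot apply.

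**The case against.** The strongest reply is that the plan already contains the right comparison. The Bayesian models compare the optimised programme with each arm of the trial, acceptance is tied to their posterior probability, and they take precedence on divergence. The propensity result is called only a marker, the protocol says that small numbers will not be definitive, and the shared advice arm means the rule carries some indirect information. All of this stands. A reader might infer that the plan never compares optimised with original BOOST. The documents do not support that, and the fault is in the propensity part alone. What the reply leaves open is that this part is also written as a ground of its own for keeping the original programme, and that it omits the standard error of the comparison it implies.

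A second tempting reading is that weighting on a long covariate list discards about half the cohort, or doubles the variance of the estimate. Weighting removes nobody, and the loss of effective size depends on the weight target, the number of covariates and the imbalance, none of which the protocol fixes. Simulations with 24 treated patients, 100–200 controls, 3–15 covariates and imbalances of 0–0.4 SD gave 24–92% of the effective size retained under weights targeting the pooled population. Under weights targeting the enrolled cohort, the optimised group keeps 100%. The protocol also plans sensitivity analyses of model specification, and the final covariate list and weight details may properly sit in the SAP. What remains is a risk of extreme weights when the list is long and treated patients are few.

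**Conclusion.** The point holds for the propensity analysis. The protocol fixes the advice arm as the comparator and fixes a rule that judges optimised against original BOOST without the cohort's own uncertainty. This is stated text, not detail left to an SAP, and it falls short of the comparison with the BOOST group promised in the same section.

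With 24 patients, a truly equal programme would meet the ground for keeping the original about 11–20% of the time by chance. A programme 0.2 SD worse would reach the midpoint or higher 17–19% of the time. These figures rest on assumed arm sizes and normal theory. They exclude confounding and any loss of precision from weighting, which would widen the uncertainty. The consequence is moderated by the Bayesian precedence rule, but that rule conflicts with the *or* condition and the text does not say which applies. No particular loss of patients or inflation of variance can be claimed from the documents.

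**What to change.** 1. For the optimisation question, make the original BOOST arm the propensity comparator and weight the historical patients to the enrolled cohort (optimised patients weight 1, historical patients PS/(1 − PS)). Keep the advice arm as a secondary comparison.
2. Report optimised minus original with its 95% interval, and base the propensity marker on that estimate and interval in place of the upper-half and below-lower-limit rules.
3. Reconcile the *or* condition with the sentence giving the Bayesian analysis precedence.
4. Use the same direct contrast for the Stage 2 benchmark.
5. Keep the propensity score to a short list of prognostic variables, and report balance and effective sample size.

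The cost is wording and a little code. Section 9.6.2 (Data processing) confirms that the trial data used for the synthetic controls will be held by the study team. The downside is that the reported interval will be visibly wide, and the effect will refer to the enrolled cohort rather than to the trial population or a pooled one.

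### The Stage 1 accept/reject rule reads a single probability, but there are two unranked primary outcomes, so when they split it says both accept and keep the original

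*Protocol*

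**What the plan says.** Protocol section 8.2 sets the outcome hierarchy as "Primary outcomes: ODI walking item and the 6-minute walk-test". The next line ranks the rest: "Secondary outcomes listed in order of priority: ODI standing item, ODI pain item, ODI overall, followed by all remaining outcome measures". The two primaries carry no order there, nor in the Study Summary or section 4.2, which name both as measures of walking capacity.

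Under Final decisions in section 8.2, the team is to weigh a "posterior probability that the optimised intervention has improved outcomes from the Bayesian analysis and accept the new intervention if this is above 50" per cent. The opposite clause begins "If this probability estimate is below 50% or the point estimate from the propensity score analysis is lying below the original lower limit", and its consequence is that the original programme continues. Both clauses are in the singular and neither names an outcome. The propensity marker likewise refers to one point estimate, set against the confidence interval of the original trial.

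The only conflict rule is "If the two analyses diverge, the Bayesian approach will be taken as the primary analysis as it will be more sensitive". It settles a disagreement between methods, not between outcomes. The therapist interviews are to be triangulated with the results, but no rule across outcomes follows from that.

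**The concern.** The protocol itself fixes the accept clause, the reject clause, the threshold and a tie-break. The models yield one posterior probability for each primary outcome. If the ODI walking item gives a value above 50% and the walk test a value below it, the accept clause and the reject clause are both satisfied by the same data.

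A split is plausible. One outcome is a self-reported questionnaire item and the other is a walk test recorded by the therapist (section 6.1). Stage 1 determines whether the optimised or the original programme goes forward, and the online course in Stage 2 is meant to teach the optimised one (section 2). Without a stated rule, the outcome that decides can be picked once both results are known, and reading *either* instead of *both* changes how easily an unimproved programme is accepted.

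**Working it through.** The protocol states no power, error rate or other operating characteristic for this rule, so there is no figure to reproduce. The calculation below sizes the ambiguity in the 50% rule only. The propensity rule has the same gap but is not sized.

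**Inputs from the protocol**
- Threshold 50%, written for one probability (section 8.2).
- Two unranked primary outcomes (section 8.2).
- New patients: 24 (Study Summary), or 24 + 6 = 30 on one reading of section 8.1.

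**Assumptions, because the protocol gives no figures**
- Near-neutral prior and roughly normal posterior, so a probability above 50% means that the estimate lies on the favourable side of zero.
- Correlation ρ between the two estimates from 0 to 0.9. Effects are oriented so that positive favours the optimised programme.
- Historical BOOST group arm of 100 to 300 patients.
- No allowance for centre effects, covariate adjustment or the borrowing priors.

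**No true difference on either primary**
- P(both pass) = 1/4 + asin(ρ)/(2π)
- P(at least one passes) = 3/4 − asin(ρ)/(2π)
- P(split) = 1/2 − asin(ρ)/π

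At ρ = 0.5, asin(0.5) = π/6, so both = 1/4 + 1/12 = 0.333, either = 3/4 − 1/12 = 0.667, and split = 1/2 − 1/6 = 0.333.

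| ρ | one named primary | both | either | split |
|---|---|---|---|---|
| 0 | 50% | 25% | 75% | 50% |
| 0.3 | 50% | 30% | 70% | 40% |
| 0.5 | 50% | 33% | 67% | 33% |
| 0.7 | 50% | 37% | 63% | 25% |
| 0.9 | 50% | 43% | 57% | 14% |

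**True gain of 0.2 SD on both primaries**

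SE = √(1/n + 1/n_hist). With n = 24 and n_hist = 200, SE = √(0.0417 + 0.0050) = 0.216, and one primary passes with probability Φ(0.2/0.216) = Φ(0.926) = 0.82. The bivariate normal at ρ = 0.5 gives both 0.72, either 0.93 and split 0.21.

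Over n = 24 to 30 and n_hist = 100 to 300:
- split: 18% to 22% at ρ = 0.5, and 8% to 10% at ρ = 0.9;
- at ρ = 0.5 with n = 24: both 70% to 73%, one primary 81% to 83%;
- at ρ = 0.5 with n = 30: both 73% to 76%, one primary 83% to 85%.

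With a gain of 0.3 SD (n_hist = 200), the split falls to 9% to 12% at ρ = 0.5 and 4% to 5% at ρ = 0.9.

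**True loss of 0.2 SD on both primaries** (n = 24, n_hist = 200, ρ = 0.5). By symmetry, *either* accepts 1 − 0.72 = 28% of the time, *both* accepts 1 − 0.93 = 7%, and one named primary accepts 1 − 0.82 = 18%.

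**The case against.** A statistical analysis plan, not at hand, may say how the primaries combine, and the phrase about improved outcomes could simply mean both of them. The decision is also not purely mechanical: section 8.2 says that the small sample will not be definitive, that the analyses help to inform an assessment, and that interview findings will be weighed. These points reduce the weight of the finding. They do not remove it, because the protocol already commits to numerical accept and reject clauses that conflict when the primaries split, and the declared discretion does not say how to resolve that.

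The size also needs restraint. Both primaries measure walking capacity, so a high correlation is plausible, and the 33% split assumes no true difference. Most of the 67% acceptance under *either* comes from the 50% threshold itself, since one named primary already accepts half the time.

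Two stronger readings are tempting. A reader might infer that a responder result is a third decision criterion, because section 8.2 mentions probability statements on "whether a greater proportion of people achieve clinically significant outcomes in pain and walking with the improvements". The text presents this as an advantage of the Bayesian framework and does not tie the 50% rule to it. A reader might also infer that the advice arm competes as comparator, because "Bayesian hierarchical linear models will be used to compare the optimised intervention to each arm of the BOOST trial". However, the question is whether the optimisation improved the intervention, and the alternative is to continue with the original, so the original BOOST group arm is the natural reference.

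**Conclusion.** The point holds for the two declared primaries. As written, the Stage 1 rule gives contradictory instructions whenever they fall on opposite sides of 50%, and the propensity criterion leaves the same question open. When the primaries agree, the gap has no effect.

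Under the assumptions above, a split is neither rare nor the usual case: about one time in three with no true difference at correlation 0.5, and about one in five with a 0.2 SD gain. Both rates are lower if the outcomes are highly correlated. Choosing between *either* and *both* moves acceptance of an unimproved programme by 17 points up or down from the 50% that a single named primary would give. The documents do not support counting pain and walking responders or the advice arm as further criteria. The rule should be corrected before the data are seen, but the data remain analysable either way.

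**What to change.** In Final decisions (section 8.2), state before the data are seen that:
- the 50% rule applies to the ODI walking item and to the 6-minute walk test, each against the original BOOST group arm;
- the propensity point-estimate rule also applies to each primary, set against the original trial's interval for that same outcome;
- the optimised programme is accepted only if both primaries pass, and the original is kept if they disagree.

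This fits the protocol's own clause that a probability below 50% means continuing with the original. Naming the comparator in the same sentence makes explicit what the text already implies.

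The change is one of wording and needs no new data. Its price is power: for the 50% rule with 24 new patients and correlation 0.5, a programme truly better by 0.2 SD on both primaries would be accepted about 71% of the time, against about 82% on one primary. Applying the propensity rule to both outcomes could lower this further, and that is not sized here. If the sponsor finds the price too high, one named lead primary or a joint posterior probability, fixed in advance, would also remove the contradiction.

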4 RESEARCH QUESTION/AIM(S)

4.1 Aims

Stage 1

Stage 1 aims to evaluate the feasibility and effectiveness of the optimised BOOST programme in relation to the results from the BOOST RCT.

Stage 2

Stage 2 aims to i) develop and launch the BOOST MOOC and assess therapist learning and implementation outcomes and ii) evaluate patient outcomes in a subset of learners that commit to implementing the BOOST programme, to ensure outcomes are the same or better than the original BOOST programme.

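### The Stage 2 launch rule treats a non-significant difference from the original trial as success, with no margin, so it cannot show that outcomes are the same or better

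*Protocol*

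**What the plan says.** Protocol section 4.1 gives the patient-outcome aim of Stage 2 as "to ensure outcomes are the same or better than the original BOOST programme". Section 8.2, under the Stage 2 patient outcomes, turns this into a decision rule. The decision at stake is worded "For implementation to be deemed successful and be launched widely via the FutureLearn BOOST MOOC". The condition set for it reads "the benchmark will be that the estimates of changes in pain-related disability and walking are not significantly worse than the original trial". As comparator, the same sentence names synthetic controls built from the earlier trial's data.

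On size, section 8.1 says "We will recruit a minimum of 60 patients and 10 therapists", with no power or precision argument. Section 8.2 says "We will collect outcome data from a minimum of 60 participants".

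On method, Stage 2 will "follow the same data analysis plan as described for Stage 1". That means propensity-weighted mixed models with centre random effects, plus Bayesian hierarchical models that borrow from the original trial. If the two diverge, "the Bayesian approach will be taken as the primary analysis as it will be more sensitive".

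The benchmark comes with no margin, significance level, interval or posterior threshold, and the protocol does not say whether every named outcome has to meet it.

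**The concern.** The aim is in substance a non-inferiority claim, but the rule attached to it is a failed test of inferiority. Such a test can fail because delivery after online training is as good as before, or because the data are too imprecise to tell. The rule counts both as success.

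It also rewards imprecision. Fewer patients, more missing follow-up, stronger centre effects or more variable weights all widen the interval and make a pass more likely.

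The decision to launch the course widely rests on this rule. A pass could be read as showing that the original benefit has been kept when the data do not show it. The rule is written into the protocol. An SAP could define the word significantly, but adding a margin would replace the rule.

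**Working it through.** **Nothing to reproduce.** The protocol states no power, significance level, margin or detectable difference for Stage 2.

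**Inputs from the protocol.** At least 60 patients and 10 therapists (8.1), a target of 10 sites (7.2), and centre random effects (8.2).

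**Assumptions, because the protocol gives no figure.**
- Comparator: the original BOOST arm, with 100 to 300 patients (base case 200).
- True loss d: 0.2 to 0.4 SD. Section 1.2 says only that the 6-month ODI benefit was modest and that walking improved significantly.
- Analysed patients: 60, or 51 after an assumed 15% loss (60 × 0.85).
- ICC: 0 to 0.05.
- Test: two-sided 5%.

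**Formulas (SD units).** n_eff = n / [1 + (m − 1) × ICC], with m = n/10. SE = √(1/n_eff + 1/n_hist). Chance of passing = 1 − Φ(d/SE − 1.96).

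**Worked example.** For n = 60, ICC = 0 and n_hist = 200, SE = √(0.01667 + 0.005) = 0.147. At d = 0.3, d/SE = 2.04 and the chance of passing is 1 − Φ(0.08) = 47%.

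**Chance that one outcome passes despite a true loss**

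| n, ICC, n_hist | n_eff | SE | d = 0.2 | d = 0.3 | d = 0.4 |
|---|---|---|---|---|---|
| 60, 0, 300 | 60 | 0.141 | 71% | 44% | 19% |
| 60, 0, 200 | 60 | 0.147 | 73% | 47% | 22% |
| 60, 0.05, 200 | 48 | 0.161 | 76% | 54% | 30% |
| 51, 0.05, 100 | 42.3 | 0.183 | 81% | 63% | 41% |

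The first and last rows are the extremes of the assumed range. With a one-sided 5% test (60 and 200 patients, no clustering) the figures fall to 61%, 35% and 14%.

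**If two outcomes must both pass.** Simulation with 60 and 200 patients, no clustering, both outcomes losing d and a correlation of 0.3 to 0.7 gives 56-62%, 27-34% and 8-13% at d = 0.2, 0.3 and 0.4.

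**Direction with sample size** (d = 0.3, 200 historical patients, one outcome, no clustering)

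| Stage 2 patients | 20 | 60 | 120 | 240 |
|---|---|---|---|---|
| Chance of passing | 75% | 47% | 26% | 12% |

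The sizes other than 60 only show the direction. They are not forecasts for this study.

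**The same 60 patients under a margin rule.** Success requires the 95% interval to exclude a loss of M. With no true loss, the chance of success is Φ(M/SE − 1.96), with SE = 0.147.

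| Margin M (SD) | 0.10 | 0.15 | 0.20 | 0.30 | 0.40 |
|---|---|---|---|---|---|
| Success when nothing is lost | 10% | 17% | 27% | 53% | 78% |

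When the true loss equals M, success falls to 2.5%. For 80% power against 200 historical patients, Stage 2 would need about 65 patients at M = 0.4 and about 155 at M = 0.3. At M = 0.2 it would need about 10,400, which is out of reach.

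**The case against.** **The percentages are not the study's own.** They come from an unadjusted comparison of two means. The planned models adjust for baseline, weight, include centre effects and borrow historical data, which move precision in different directions. This stands: the figures are illustrations.

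**A stronger reading is tempting.** A reader might infer that the rule passes about half to four-fifths of the time once the benefit is gone, or that a large loss will usually go unnoticed. The documents support neither. They give no size for the original benefit, and at 0.4 SD, the largest loss modelled, the rule passes only 19-41% of the time, so the loss is usually caught. The benchmark also names more than one outcome, and if all must pass the rates drop further.

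**Sixty is a minimum with outcome data.** Section 8.2 says so, and section 9.6.2 provides for posting outcome measures to people who miss the 6-month visit, although that cannot recover the walk test. The 51-patient case is therefore a sensitivity case. The pattern does not depend on it: 60 analysed patients without clustering still give 71-77%, 44-55% and 19-31% over 100 to 300 historical patients.

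**The protocol admits limits and has a Bayesian analysis.** The caveat that small numbers are not definitive sits with the Stage 1 decisions and does not turn non-significance into evidence of similarity. The Bayesian analysis takes priority on divergence, but the protocol does not say what significantly worse means in that model. The 50% posterior threshold in Stage 1 concerns improvement, which is a different question.

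**Sixty patients are too few for a margin rule.** Largely true for small margins, as the last table shows. That is a reason to allow an inconclusive result. It does not justify counting one as success.

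**Conclusion.** The launch rule is wrong as written and must be changed. It has no margin, it cannot support the aim in section 4.1, and it passes more easily as precision falls. These three points follow from the text and need no assumed effect size.

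The size is conditional. Under the assumptions listed, the rule passes roughly 20-80% of the time per outcome for a true loss between 0.4 and 0.2 SD, and less often if all named outcomes must pass. Confidence is high in the defect and limited in the percentages. The protocol ties the rule to a wide launch; a reader should not take that to mean a national one.

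**What to change.** Before any Stage 2 data are seen, amend section 8.2 as follows.

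1. For each outcome named in the benchmark, state the largest acceptable loss against the original BOOST arm, for example as a fraction of the original 6-month effect.
2. Say whether all named outcomes must pass.
3. Declare success only if the interval excludes a larger loss, or if the Bayesian model already planned gives a stated high posterior probability that the loss is smaller than the margin. Say which of the two decides.
4. Otherwise report the result as inconclusive.

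At a minimum, report the interval, describe a non-significant result only as not shown to be worse, and do not treat it as showing that outcomes are the same or better.

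**Cost.** Protocol and SAP wording, and one margin per outcome. Adopting the rule needs no extra patients, but success becomes much harder to claim. With 60 patients, 200 historical patients and no clustering, a programme that has lost nothing would meet a margin of 0.2, 0.3 or 0.4 SD only about 27%, 53% or 78% of the time, and half those margins 10-27% of the time. Inconclusive may therefore be the most likely verdict. The protocol should say in advance what 60 patients can show against the chosen margins.
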